## **11 STUDY MANAGEMENT**

### **11.1 Investigator/Site Selection**

MIVI Neuroscience or its Contract Research Organization (CRO)/designee are responsible for conducting a Selection/Qualification Visit with potential investigational sites, if deemed necessary, to determine if the investigator and investigational site meets the criteria for conducting the clinical investigation. The Selection/Qualification Visit may be in person, over the phone, based on previous experience with the site, or a combination thereof. The site screening and qualification results will be documented, and a participation decision communicated to the potential site.

### **11.2 Site Initiation and Training**

A Site Initiation Visit will be conducted and documented to train the study staff on study conduct prior to enrollment in the study. Documentation of study specific training and study role will be documented. Training will include the specifics of study conduct, device-specific information, and adverse event reporting. A sponsor representative may be present at the procedure to provide additional training and support.

Prior to enrolling patients at an investigational site, all required documentation must be completed.

### **11.3 Q Aspiration Catheter Devices**

The Q Aspiration Catheter is a CE Marked device used according to the IFU, therefore device may be shelf stock. A site may be supplied with devices for study. If device is supplied to the site, the investigator or delegated personnel must maintain records of the product delivery to the site, the inventory at the site, the use, and the return to the sponsor.

### **11.4 Clinical Study Management Responsibilities**

The sponsor's clinical department personnel or a sponsor representative(s) will have overall study management responsibility including on-site consultation to assist with technical support, protocol adherence, assurance of the accuracy of case report forms, and compliance with applicable regulations. The contact information for the study sponsor is:

### **11.5 Case Report Forms (CRFs)**

The sponsor or designee will provide case report forms for the study. Case report forms must be completed to capture each enrolled subject's study data either on paper or electronically. The source data (paper or electronic) includes and is not limited to the information contained in original medical records and certified copies of results, test results and printouts, patient questionnaires, source worksheets, and electronic monitoring data. Data queries will be routed to the investigational site to resolve any data discrepancies. The site should respond to the query within 10 working days. Investigators will be responsible for acknowledging the completeness and accuracy of the data by signing, either electronically or on paper, CRFs where indicated.

### **11.6 Study Monitoring**

The investigational site will be monitored to ensure compliance with the study protocol, adherence to applicable regulations, and accuracy of study data. MIVI Neuroscience and/or its CRO/designee will monitor the study by frequent communications with and visits to each clinical site to ensure the trial is conducted in accordance with this clinical protocol and the law.

The study monitor(s) will be responsible to complete a review of regulatory documents, source documents, and case report forms for accuracy, completeness, and legibility. Site monitoring visits will be documented in a written monitoring report to include the identification of any follow-up items or concerns. Resolution of follow up items and concerns will also be documented in the monitoring report.

The investigator will permit the sponsor and/or agent from the relevant regulatory authority or appointed member from the IEC, or equivalent, if requested, to inspect all case record forms and corresponding portions of the study patients' original office and/or hospital records.

### **11.7 Core Laboratories**

An independent angiographic core laboratory will be utilized for this study to interpret all angiographic data gathered on all study subjects and determine mTICI scores. The core lab data must be de-identified and labeled with subject number and date of procedure and then forwarded to the core lab. Refer to Core Laboratory Manual for additional information.

### **11.8 Trial Termination/Investigational Site Termination**

MIVI Neuroscience, Inc. may terminate this trial at any time. MIVI Neuroscience also reserves the right to terminate an Investigational Site if that site fails to comply with the Clinical Trial Agreement, EU Regulations, submits falsified or unreliable data, or misuses the device.

### **11.9 Trial Registration**

This study will be registered on [www.clinicaltrials.gov](http://www.clinicaltrials.gov).

## 12 RECORDS AND REPORTS

### 12.1 Essential Documents

Investigators are required to provide MIVI Neuroscience the following information prior to subject consent at the investigational site:

- Copy of investigators' curriculum vitae [principal investigator and co-investigator(s)]
- Signed Clinical Trial Agreement
- Copy of the EC approval letter and
- EC approved informed consent document
- Appropriate training documentation

### 12.2 Investigator Records

The investigator is responsible for the preparation, review, and retention of the records listed below:

- All pertinent correspondence that pertains to the investigation
- Signed and dated informed consent forms
- Serious adverse event information
- Medical history (medications etc.), medical records, progress notes, hospital charts, etc.
- A record of each patient's exposure to the investigational device (e.g. implant, follow up, etc.)
- Documentation of any deviation from protocol
- Signed Investigator's Agreement and curriculum vitae
- The protocol and any amendments

Records are pertinent to regulatory authority's inspection and must be retained for a minimum period of (2) years after the latter of two dates: 1) the date on which the investigation is terminated or completed, or 2) as long as local regulatory authorities in countries conducting the research study require retention.

### 12.3 Sponsor Records

MIVI Neuroscience or its designee will maintain the following records:

- all pertinent correspondence which pertains to the investigation,
- device shipment records and disposition logs (if applicable),
- signed Clinical Trial Agreements and curriculum vitae for each Investigator,
- adverse events and complaints,
- all data forms, prepared and signed by the investigators, received source documentation and core lab reports,
- investigational plan and report of prior investigations,
- site monitoring reports, and
- final reports.

## 13 PROTOCOL DEFINITIONS

### 13.1 Abbreviations

ADE	Adverse device effect; also UADE (unanticipated adverse device effect)
AE	Adverse Event; also SAE (serious adverse event)

ASPECTs	Alberta Stroke Program Early CT score
BP	Blood Pressure
CA	Competent Authority
CEC	Clinical Events Committee
CRF/eCRF	Case Report Form/electronic Case Report Form
CT/CTA	Computerized Tomography / CT Angiography
CV	Curriculum Vitae
EC	Ethics Committee
ENT	Embolization to a new territory
ICF	Informed Consent Form
(s) ICH	(Symptomatic) intracranial hemorrhage
ICH GCP	International Conference on Harmonization E6 Guidelines for Good Clinical Practice
IFU	Instructions For Use
LR/LAR	Legal Representative/ Legally authorized representative
MRI/ A	Magnetic Resonance Imaging/ Angiogram
mRS	modified Rankin Score
NIHSS	National Institutes of Health Stroke Scale
SAE	Serious Adverse Event
mTICI	Modified Thrombolysis in Cerebral Infarction (Scale)
tPA	Tissue Plasminogen Activation
UADE	Unanticipated Adverse Device Effect

### 13.2 Study Endpoint Definitions

**Primary Performance Endpoint** of successful revascularization defined as mTICI flow 2b-3 in the target vessel at the end of the procedure as determined by an independent Angiographic Core Laboratory.

**Primary Safety Endpoint** of Symptomatic Intracranial Hemorrhage (SICH) –

Defined according to ECASS II definition of any apparently extravascular blood in the brain or within the cranium associated with clinical deterioration, as defined by an increase of 4 points or more in the score on the National Institutes of Health Stroke Scale (NIHSS), or that leads to death and is identified as the predominant cause of the neurologic deterioration. This endpoint is assessed from data obtained within 24 hours post procedure (0-36 hrs).

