### 4.2 Primary Endpoints

The primary performance endpoint is successful revascularization defined as final mTICI 2b-3 flow in the target vessel.

The primary safety endpoint is symptomatic intracranial haemorrhage at 24 hours post-procedure as detected by CT scan/MRI with an NIHSS change of greater than or equal to 4.

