### **6.3 Inclusion Criteria**

Subjects who meet the following criteria may be included in the study:

1. Age 18 to 85 years;
2. Diagnosis of acute ischemic stroke with mechanical thrombectomy procedure < 8 hours from onset of symptoms or last known well;
3. Large Vessel Occlusion on CT scan or MRI in the Anterior Cerebral Vasculature up to A1, M1, M2, or Posterior Cerebral Vasculature;
4. ASPECTS 6 – 10 or volume of diffusion restriction < 50 mL;
5. Use of the Q Aspiration Catheter as the first line treatment according to the IFU;
6. Signed informed consent by patient or legally authorized representative.

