## **8.3 Mechanical Thrombectomy Procedure**

To be eligible to participate, the procedure had to begin within 8 hours of stroke onset with planned first line therapy of the use of the Q Aspiration Catheter alone.

Digital subtraction angiography should have been undertaken to verify vessel occlusion using diagnostic angiography and contrast agent. Repeat diagnostic angiography should have been done on the treated region to assess recanalization grade per mTICI criteria after Q Catheter use and at the end of the procedure.

The Q Aspiration Catheter must be used per the Instructions for Use to be eligible for participation. Per the IFU, the Q Aspiration Catheter may be used with three aspiration attempts.

Procedural data collection will include:

- General procedural data (anesthesia use, procedure start time, revascularization time and end time, thrombolytic therapy administered, ancillary device use)
- Target vessel location
- Pre-and post-procedure target vessel flow information
- Q Aspiration Catheter use during the procedure
- Rescue device use, if applicable
- Treatment outcome
- Embolization to a new territory
- Procedure and device-related adverse events or any device related problems
- De-identified procedural angiogram should be collected for the Core Lab (only after subject consent) (see Section 11.7)

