### Secondary Endpoints

- Successful revascularization defined as mTICI 2b-3 with the Q Aspiration Catheter as determined by an independent Angiographic Core Lab.
- Embolization to a new neurovascular territory during the procedure as determined by the Core Lab
- Good functional outcome measured by Modified Rankin Score of 0-2 at 90 days
- All-cause mortality at 90 days

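### Neither mTICI endpoint takes account of flow before the Q catheter is used, so a vessel already at 2b or better that stays there counts as a success

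*Combined protocol and SAP*

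**What the plan says.** **Endpoints.** Section 4.2 states: "The primary performance endpoint is successful revascularization defined as final mTICI 2b-3 flow in the target vessel". Section 13.2 adds the time point and the reader: "successful revascularization defined as mTICI flow 2b-3 in the target vessel at the end of the procedure as determined by an independent Angiographic Core Laboratory". The secondary endpoint in section 13.2 reads "Successful revascularization defined as mTICI 2b-3 with the Q Aspiration Catheter as determined by an independent Angiographic Core Lab", and section 4.3 makes clear that this means flow after the Q catheter alone. The synopsis and section 10.1 restate the primary endpoint on the same basis. None of these places mentions flow before treatment.

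**Entry.** Section 6.3 requires "Large Vessel Occlusion on CT scan or MRI in the Anterior Cerebral Vasculature up to A1, M1, M2, or Posterior Cerebral Vasculature". No exclusion in section 6.4 concerns angiographic flow. Section 8.2 records hospital transfer and thrombolytic therapy at baseline, and neither is an exclusion.

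**Angiography.** Section 8.3 says: "Digital subtraction angiography should have been undertaken to verify vessel occlusion using diagnostic angiography and contrast agent". It names repeat angiography "to assess recanalization grade per mTICI criteria after Q Catheter use and at the end of the procedure", and lists "Pre-and post-procedure target vessel flow information" among the data to be collected. Under section 11.7 the core laboratory is "to interpret all angiographic data gathered on all study subjects and determine mTICI scores".

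**Analysis.** Section 10.2 analyses everyone who consented, describes the endpoints and other collected data, and sets the endpoints against published outcomes without a formal test. Section 10.3 puts all subjects of that population into the primary analysis of the primary endpoints.

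**The concern.** Section 4.1 gives the study's purpose as demonstrating safety and performance of the Q catheter in removing clot. A rate meant to show this should separate vessels that were reopened from vessels that were already open. Flow can change between the qualifying CT or MRI and the first angiogram, through thrombolysis, spontaneous clearing or migration of the clot. A subject who reaches mTICI 2b in that interval, is then aspirated for residual clot and ends unchanged at 2b satisfies both endpoint definitions.

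With a single arm there is no control group in which the same prior clearing would show up. The Q-alone endpoint is the more exposed of the two because it attributes the result to the catheter. The primary endpoint is final flow and, given the definition of rescue therapy in section 13.3, may include the effect of other devices or intra-arterial tPA.

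**Working it through.** The plan gives no target rate, alpha, power or derived sample size, so there is no figure of its own to reproduce. The check has two parts.

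**1. Does any rule bring in pre-Q flow?**

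| Place | Content | Condition on pre-Q mTICI? |
|---|---|---|
| Synopsis, 4.2, 10.1, 13.2 (primary) | 2b-3 at end of procedure | None |
| Synopsis, 4.3, 13.2 (secondary) | 2b-3 after the Q | None |
| 6.3, 6.4 | Occlusion on CT or MRI | None |
| 8.3 | Angiography expected to confirm the occlusion | No grade and no stated consequence |
| 8.3 | mTICI after the Q and at the end | Pre-Q grading not named |
| 10.2, 10.3 | All consented subjects | None |

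Section 8.3 words the angiographic check as an expectation. In the same section the 8-hour start and use according to the IFU are worded as eligibility conditions. Screening happens after the procedure (section 8.1), so the check describes care already given.

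**2. How large could the effect be?**

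Inputs:
- N = 50, the maximum in section 6.2.
- x = observed successes (assumed).
- k = subjects at 2b or better before the Q who all remain successes (assumed; the documents give no frequency).

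All-subjects rate: x/N. Restricted rate: (x − k)/(N − k). The drop is k(N − x)/[N(N − k)].

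Q-alone endpoint, assumed 30/50 = 60.0%:
- k = 2: 28/48 = 58.3%, drop 1.7 points
- k = 4: 26/46 = 56.5%, drop 3.5 points
- k = 6: 24/44 = 54.5%, drop 5.5 points

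Final flow, assumed 40/50 = 80.0%:
- k = 4: 36/46 = 78.3%, drop 1.7 points

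Equivalently, the all-subjects rate exceeds the restricted rate p by (k/N)(1 − p). For k = 1, 3 and 5 this is 0.6, 1.8 and 3.0 points at p = 70%, and 0.2, 0.6 and 1.0 points at p = 90%. The excess shrinks as the restricted rate rises.

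For scale, the Clopper-Pearson 95% interval for 40/50 is 66.3% to 90.0%, a half-width of about 12 points.

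**Direction.** If one subject at 2b before the Q worsened to 2a and was scored a failure, setting that subject aside would turn 40/50 = 80.0% into 40/49 = 81.6%. The gap can therefore also lower the rate.

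**The case against.** The strongest answer is that section 8.3 already deals with most of this. It expects angiographic confirmation of the occlusion, section 6.1 defines the population as large vessel occlusion treated by aspiration, and a vessel confirmed as occluded would usually grade below 2b. This stands, and it confines the gap to vessels that were partly open, or not checked, at the first angiogram. It does not close the gap, because no grade is attached to the check and nothing follows if the vessel is found open. Section 13.3 also grades 2B by the share of territory filled without defining the territory, so the text does not settle how a confirmed M2 branch occlusion would grade.

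Other points that stand:
- Section 10.2 covers other collected data, so pre-procedure flow may well be summarised. What is missing is its use in scoring.
- The Core Lab Manual (Reference B) is not part of the text and may call for baseline grading. The definitions in section 13.2 would still not use it.
- No hypothesis is tested, and the shift is well inside the sampling uncertainty. However, a confidence interval does not reveal a bias that runs mainly one way.
- Restricting the primary endpoint itself would conflict with section 10.3. If the published rates use final flow, it would also make the comparison less like-for-like. The documents do not say how those rates are defined.

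A reader might go further and infer that partly cleared clots are routinely credited to the device, or that the error can only raise the rates. The documents support neither. They give no frequency and expect the occlusion to be confirmed, a vessel that worsens from 2b counts as a failure, and the primary endpoint is not a device-only measure.

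**Conclusion.** The gap is real but limited. Neither mTICI endpoint requires the vessel to be below 2b before the Q is used, and the pre-procedure flow that is collected enters no success rule. Subjects already at 2b or better who stay there count as successes, most consequentially for the Q-alone rate.

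The size rests entirely on assumed counts: 1.7 to 5.5 points on a 60% Q-alone rate for 2 to 6 of 50 subjects, and 1.7 points on an 80% final rate for 4 of 50, provided all of them remain successes. The direction is usually upward. This justifies an added, pre-specified analysis. It does not justify replacing the primary endpoint.

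**What to change.** Keep the all-subjects rate as the primary analysis, in line with section 10.3. In sections 13.2 and 10.3, add the following:

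1. The core laboratory grades pre-Q mTICI from the angiograms it already receives, and the distribution of those grades is reported.
2. For both mTICI endpoints, a second pre-specified rate is given, restricted to subjects whose core-lab pre-Q mTICI is below 2b.
3. The number of subjects at 2b or better before the Q, and the number with no readable pre-Q angiogram, are each reported separately.

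If the Core Lab Manual already provides for baseline grading, the first item needs only a cross-reference.

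The cost is one extra core-lab field and a second rate on slightly fewer subjects, which may look slightly less favourable. The restricted rate still credits the treatment with any clearing before the Q that stopped short of 2b. The distribution of pre-Q grades lets a reader see how many subjects started at 1 or 2a.

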### Secondary Endpoints

- Successful revascularization defined as mTICI 2b-3 with the Q Aspiration Catheter as determined by an independent Angiographic Core Lab.
- Embolization to a new neurovascular territory during the procedure as determined by the Core Lab
- Good functional outcome measured by Modified Rankin Score of 0-2 at 90 days
- All-cause mortality at 90 days

### 13.3 Protocol-specified and Other Definitions

#### Device Failure

The device is used in accordance with the IFU but does not perform according to IFU and negatively impacts the treatment.

#### Device Malfunction

An unexpected change to the device that is contradictory to the IFU and may or may not affect device performance.

### Rescue therapy

The use of another mechanical thrombectomy device, mechanical pump aspiration, intracranial stenting, or initiation of intra-arterial tPA during the procedure after a failure to recanalize with the study device.

### Modified TICI Flow

Thrombolysis In Cerebral Infarction scale (classification of cerebral artery flow) -

- 0 No perfusion or anterograde flow beyond site of occlusion
- 1 Penetration but not perfusion. Contrast penetration exists past the initial obstruction but with minimal filling of the normal territory
- 2 Incomplete perfusion wherein the contrast passes the occlusion and opacifies the distal arterial bed but rate of entry or clearance from the bed is slower or incomplete when compared to non-involved territories
  - 2A Some perfusion with distal branch filling of <50% of territory visualized
  - 2B Substantial perfusion with distal branch filling of  $\geq 50\%$  of territory visualized
  - 2C Near complete perfusion except for slow flow in a few distal cortical vessels, or presence of small distal cortical emboli
- 3 Complete perfusion with normal filling of all distal branches

## 14 INVESTIGATIONAL PLAN HISTORY

Revision	Date	Change(s)
DRAFT	OCT2018	Changed study type from a prospective, single arm study to an observational study.
A	14MAR2019	Initial Release
B	01AUG2019	Changed the FU visit from office to either office or telephone visit, deleted NIHSS at FU visit, minor edits for clarity, and added mTICI 2C definition.

